10.2. Adverse Events

Adverse events will be classified into SOC and PT using MedDRA version 20.0 or higher. Treatment-emergent adverse events (TEAEs) are defined as events beginning or worsening on or after the date of first dose of study medication. If the start date of the event is incomplete or missing, the event will be categorized as a TEAE unless sufficient information (from partial start date, or from end date) clearly indicates that the event started prior to the date of first dose. If event severity or relationship to study intervention is missing, the event will be summarized at the worst possible severity (severe) and strongest possible relationship (very likely/certain).

All events attributed to the application of Vaseline during the Baseline visit will be noted in the verbatim event term by the investigator and identified programmatically from the verbatim term. All such events will be listed by patient, and summarized by SOC and PT overall, since patients

are not randomized to treatment at the time of Vaseline application. AEs attributed to application of Vaseline will also be listed.

Adverse events will be listed by subject, event, and date, with non-TEAEs flagged in the listings, as follows:

- All adverse events
- All serious adverse events (SAEs)
- Adverse events leading to drug withdrawal

TEAEs will be summarized by treatment as follows, using both numbers of events and number and percent of patients. Patients are counted at most one-time per SOC and at most one time per PT, at the highest recorded severity or relationship (where applicable). A patient with multiple events within an SOC or PT will have all events reflected in the total numbers of events in that classification.

- Overall summary of events and patients with different types of TEAEs.
- Summary of TEAEs by SOC and PT.
- Summary of Ophthalmic TEAEs by SOC and PT.
- Summary of Ophthalmic TEAEs Occurring in the Study Eye by SOC and PT.
- Summary of Ophthalmic TEAEs Occurring in the Non-Study Eye by SOC and PT.
- Summary of Non-Ophthalmic TEAEs by SOC and PT.
- Summary of Serious TEAEs by SOC and PT.
- Summary of TEAEs Leading to Drug Withdrawal by SOC and PT.
- Summary of TEAEs Possibly, Probably, or Certainly Related to Study Intervention by SOC and PT.
- Summary of TEAEs by SOC, PT, and Severity.
- Summary of TEAEs by SOC, PT, and Relationship to Study Intervention.
- Summary of TEAEs by SOC, PT, and Site.
- Summary of TEAEs by PT.

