2.4. Treatment Assignment and Masking

At the Baseline visit, patients meeting all study criteria will be stratified by disease duration (<5 or 5+ years) and baseline MGS score in the study eye (<6 or 6-≤12). Patients will be randomized in a 1:1:1 ratio, within each of the 4 strata, to AZR-MD-001 0.5%, AZR-MD-001 1.0%, or placebo. The interactive web response system (IWRS) system will provide both a patient randomization number and study kit number to use for that patient.

Patients will be dispensed Vaseline (in a separate kit from study kit, and identified by a Vaseline kit number), and will administer it while onsite during the Baseline visit. Patients demonstrating the ability to correctly apply the ointment will be randomized and subsequently dispensed the

study kit (AZR-MD-001 0.5%, AZR-MD-001 1.0%, or placebo), to be administered twice weekly at home. All study kit medication will be provided in identical tubes and cartons to maintain masking of the study. The placebo packaging was designed to have the same appearance as the AZR-MD-001 treatment.

Upon database freeze, a designated team (as described in the [AZ201801 Expansion Cohort Unmasked Data Access Plan](#)) will be unmasked in order to conduct the Month 3 analyses, and those team members will not participate in study execution after unmasking. The remainder of the study personnel will be unmasked after all patients have completed Month 6, and the database has been locked.

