5.2. Key Definitions

5.2.1. Date of First Dose of Study Treatment

The date of first dose of study treatment will be the date of the Baseline visit, at which the randomized study treatment is dispensed. Patients are to be instructed to apply the first dose at home that evening. Patients who do not have confirmation of study treatment administration (defined as non-zero number of doses taken, on a study drug compliance eCRF at the Month 1.5 visit) will not have a date of first dose defined. If a patient takes zero doses before the Month 1.5 visit but does take subsequent doses, the date of first dose will reflect the date of dispensation of the first study treatment applied.

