5.2.3. Study Day

Study day is calculated as (date - first dose date of study medication +1) for dates on or after first dose, and (date - first dose date) for dates before the first dose date. Therefore, the first dose date is Study Day 1, and the day immediately prior is Study Day -1. The first dose date of study medication will be based on the application of Vaseline while onsite during the Baseline visit. The first application of randomized study medication is expected to be applied that evening.

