10.1. Extent of Exposure and Compliance

During the Baseline visit, the patient will be dispensed Vaseline, which will be administered while on site and the prospective patient will be observed by the physician or a designee. Eligible patients will also be dispensed randomized study medication (AZR-MD-001 or placebo), which will be administered twice weekly at home. Patients are expected to apply the first application of randomized study medication on the same date, in the evening.

Application, dispensation, and return of randomized study treatment will be listed chronologically by patient and visit. A separate listing of Physician Observation of Drug Application, for observation of Vaseline applied during the Baseline visit, will be provided.

Compliance for randomized study treatment, in the form of numbers of doses administered and missed, is collected in 6-week intervals. Approximately 12 doses are expected to be administered during each of those 6-week periods, but slightly more or less may be expected depending on actual visit dates and visit windows. The expected number of doses for a given period is calculated as $2 \times (\text{end date} - \text{start date} + 1) / 7$, rounded to the nearest whole number. Compliance is then calculated as $100 \times (\text{number of doses taken}) / (\text{number of expected doses})$.

Overall compliance for the 3 month study period will be based on the expected numbers of doses calculated as $2 \times ([\text{Month 3 visit date or date of discontinuation}] - [\text{date of first dose}] + 1) / 7$, for the 3 month study period, and $2 \times ([\text{Month 6 visit date or date of discontinuation}] - [\text{date of first dose}] + 1) / 7$, for the 6 month period including follow-up. The number of patients with compliance <80%, 80%-120%, and >120% will be tabulated.

For the safety follow-up period, if the final study drug is returned after the Month 6 visit (based on the visit date as compared to the final study drug return date), compliance will be calculated based on the Month 6 visit date. If dates of dispensation or return are not recorded on the eCRF (e.g., visit restrictions were in place and study treatment was mailed to patients), compliance calculations will be based on the assumption that 12 doses should have been administered.

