Table 19 Summary of Treatment-Emergent Adverse Events, by System Organ Class and Preferred Term Through Month 3 – Expansion Cohort (Safety Set)

Table 20 Summary of Treatment-Emergent Adverse Events Attributed to Vaseline Application at Baseline, by System Organ Class and Preferred Term – Expansion Cohort (Pre-Randomization Vaseline Application Set)

Table 21 Summary of Ophthalmic Treatment-Emergent Adverse Events, by System Organ Class and Preferred Term Through Month 3 – Expansion Cohort (Safety Set)

Table 22 Summary of Ophthalmic Treatment-Emergent Adverse Events, in Study Eye by System Organ Class and Preferred Term Through Month 3 – Expansion Cohort (Safety Set)

Table 26 Summary of Ophthalmic Treatment-Emergent Adverse Events, in Non-Study Eye by System Organ Class and Preferred Term Through Month 3 – Expansion Cohort (Safety Set)

Table 24 Summary of Non-Ophthalmic Treatment-Emergent Adverse Events, by System Organ Class and Preferred Term Through Month 3 – Expansion Cohort (Safety Set)

Table 25 Summary of Serious Treatment-Emergent Adverse Events, by System Organ Class and Preferred Term Through Month 3 – Expansion Cohort (Safety Set)

Table 26 Summary of Treatment-Emergent Adverse Events Leading to Study Drug Withdrawal, by System Organ Class and Preferred Term Through Month 3 – Expansion Cohort (Safety Set)

Table 27 Summary of Treatment-Emergent Adverse Events Possibly, Probably, or Certainly Related to Study Intervention, by System Organ Class and Preferred Term Through Month 3 – Expansion Cohort (Safety Set)

Table 28 Summary of Treatment-Emergent Adverse Events by Preferred Term Through Month 3 – Expansion Cohort (Safety Set)

Table 29 Summary of Treatment-Emergent Adverse Events, by System Organ Class, Preferred Term and Severity Through Month 3 – Expansion Cohort (Safety Set)

Table 30 Summary of Treatment-Emergent Adverse Events, by System Organ Class, Preferred Term and Relationship Through Month 3 – Expansion Cohort (Safety Set)

Table 31 Summary of Treatment-Emergent Adverse Events, by System Organ Class, Preferred Term and Site Through Month 3 – Expansion Cohort (Safety Set)

Table 32 Summary of Concomitant Medication Through Month 3 – Expansion Cohort (Safety Set)

Table 33 Summary of Best Corrected Visual Acuity (BCVA) Results Through Month 3 – Expansion Cohort (Safety Set)

Table 34 Summary of Vital Signs Through Month 3 – Expansion Cohort (Safety Set)

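### SAP 10.2 does not keep reactions to the pre-randomization Vaseline test dose out of the by-treatment TEAE tables

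*SAP*

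**What the plan says.** **TEAE rule.** SAP 10.2 defines TEAEs as events "beginning or worsening on or after the date of first dose of study medication". The test uses the date alone, with no criterion for cause or time of day.

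**First-dose date.** SAP 5.2.1 states: "The date of first dose of study treatment will be the date of the Baseline visit, at which the randomized study treatment is dispensed". SAP 5.2.3 gives a different basis: "The first dose date of study medication will be based on the application of Vaseline while onsite during the Baseline visit". SAP 10.3 likewise counts Vaseline as study treatment when it classifies concomitant medication.

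**Order of events.** Under SAP 2.4 Vaseline is applied on site first: "Patients demonstrating the ability to correctly apply the ointment will be randomized and subsequently dispensed the" study kit. SAP 10.1 adds: "Patients are expected to apply the first application of randomized study medication on the same date, in the evening".

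**Handling of Vaseline events.** In SAP 10.2 the investigator marks these events in the verbatim term, and a program identifies them. They are listed, and they are summarized overall rather than by arm because treatment is not yet assigned. SAP 4.5 gives them their own analysis set. Appendix 4 gives them Listing 18D and Table 20, titled "Summary of Treatment-Emergent Adverse Events Attributed to Vaseline Application at Baseline". SAP 10.2 then calls for TEAE summaries by treatment and mentions no exception for Vaseline events.

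**The concern.** A reaction to a test dose given before randomization says nothing about the assigned treatment. SAP 10.2 gives that very reason for showing these events overall. The date-only rule nevertheless makes them TEAEs, and every by-treatment TEAE table is built from TEAEs. A programmer following the text would put them in Table 20 and also in the arm-level tables.

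Safety is part of the primary objective (SAP 2.1), so the arm-level TEAE rates matter. Adding events that precede any randomized exposure raises those rates in every arm and makes active and placebo look more alike than they are.

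**Working it through.** **Step 1: apply the rule to one case.** A patient applies Vaseline at the Baseline visit, reacts on site, is randomized, and applies the assigned ointment that evening.
- Onset date is the Baseline visit date.
- First-dose date is the Baseline visit date under SAP 5.2.1 and under 5.2.3.
- Onset is on the first-dose date, so the event is a TEAE.
- The patient received a randomized dose, so the patient is in the Safety Set (SAP 4.6) and in the by-treatment tables.

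**Step 2: look for an exclusion.** SAP 4.5, 4.6, 5.2, 10.2 and Appendices 4 and 5 contain none. Table 20's title itself calls the events treatment-emergent. The Appendix 5 outputs carry forward all information from the earlier period, so the Month 6 by-treatment tables would include the events again. Appendix 5 has no counterpart to Table 20 or Listing 18D.

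**Step 3: compare the two first-dose definitions.** For most patients the dates coincide, so deleting the 5.2.3 sentence alone would not change the classification. They differ for a patient who takes no dose before Month 1.5 and starts later. SAP 5.2.1 then moves the first-dose date to the later dispensation, while 5.2.3 leaves it at Baseline. A Vaseline event in that patient is a TEAE under 5.2.3 and not under 5.2.1.

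**Step 4: size.** The plan gives no figure to reproduce. Inputs:
- n = 75 per arm, allocation 1:1:1 (SAP 2.3.1 and 2.4).
- v = proportion of patients with a Vaseline-attributed event. Assumed 2% to 8%; not in the documents.
- True TEAE incidence p: 15% on active and 5% on placebo. Assumed, for illustration only.

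Expected patients affected per arm = n × v:
- v = 2%: 75 × 0.02 = 1.5
- v = 8%: 75 × 0.08 = 6

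If Vaseline events are independent of later TEAEs, the tabulated incidence is p′ = p + v(1 − p):

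| v | Active | Placebo | Difference | Ratio |
|---|---|---|---|---|
| 0% | 15.0% | 5.0% | 10.0 points | 3.0 |
| 2% | 0.15 + 0.02 × 0.85 = 16.7% | 0.05 + 0.02 × 0.95 = 6.9% | 9.8 points | 2.4 |
| 8% | 0.15 + 0.08 × 0.85 = 21.8% | 0.05 + 0.08 × 0.95 = 12.6% | 9.2 points | 1.7 |

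The difference shrinks by the factor (1 − v): 10 × 0.98 = 9.8 and 10 × 0.92 = 9.2. The ratio moves further because the placebo rate starts low.

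**Step 5: direction.** Vaseline is applied before allocation, so v is the same in all three arms in expectation. The added events do not favour or disfavour any arm on average.

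**The case against.** The strongest reply is that the SAP already deals with these events. It flags them, gives them a set, a table and a listing, and explains why they are not split by arm. That suggests they were never meant to count against an arm. The intent is plausible, but it is not written down. Separate reporting is not exclusion, and Table 20's title points the other way.

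Several other replies stand and limit the point:
- **Bias against active drug.** A reader might infer that petrolatum reactions are charged to the active arms. They are charged to placebo equally in expectation.
- **Double counting.** A reader might infer this from Table 20. Showing a subset in its own table is ordinary; the SAP does the same for ophthalmic and serious TEAEs.
- **The related-TEAE table.** A reader might infer that Vaseline events enter it. Entry depends on the investigator's causality rating, and the Protocol 8.3.3.2 categories turn on timing relative to study drug. SAP 10.2 assigns the strongest relationship only when the rating is missing.
- **Baseline procedures.** A reader might want events from that day's dyes, Schirmer strip or gland evaluation removed too. The documents do not support this. Most of these procedures recur at later visits, the adverse event data listed in Protocol 8.3.4.1 include a date but no onset time, and counting same-date events as TEAEs is the conservative choice.
- **Overlap.** Petrolatum is the sole excipient of the active ointment and the whole of the placebo (Protocol 6.1.1). A patient who reacts to Vaseline may report the same event later, and each patient counts once per preferred term, so the patient percentages may move less than the table shows. The event counts, which SAP 10.2 also reports, have no such protection.
- **Never-dosed patients.** Those who react to Vaseline and never receive randomized treatment are outside the Safety Set and do not reach the by-treatment tables.

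**Conclusion.** The point holds as a gap in the written rule. Vaseline-attributed events meet the TEAE definition, and no passage excludes them from the by-treatment tables, contrary to the SAP's own reason for summarizing them overall. The consequence is higher absolute TEAE rates in all three arms and a slightly weaker active-placebo contrast, not a bias against active drug.

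The size depends on assumptions, since the documents give neither a Vaseline reaction rate nor an expected TEAE rate. Within the assumed 2% to 8%, the risk difference in the example falls by 0.2 to 0.8 points. These figures also assume that Vaseline events are independent of later TEAEs and that every reactor goes on to a randomized dose; departures from either would reduce the patient-level effect. The effect is probably modest, but it concerns safety tables that support the primary objective, and the remedy is cheap.

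**What to change.** 1. **SAP 10.2.** State that events flagged as attributed to the Baseline Vaseline application are excluded from the by-treatment TEAE tables unless they worsen after the first randomized dose. This covers Tables 18, 19 and 21 to 31, and Tables 18.1, 19.1 and 21.1 to 31.1. It should include the non-study-eye table, which Appendix 4 prints as Table 26 and Appendix 5 as 23.1. Report the excluded events only in Table 20, Listing 18D and the all-adverse-event listings.
2. **First-dose date.** Use one definition for TEAEs, based on randomized treatment. Reconcile SAP 5.2.3, and the Vaseline wording in 10.3, with 5.2.1.
3. **Leave unchanged.** Keep the conservative same-date rule for Baseline-date events not attributed to Vaseline. No exclusion for procedure events is needed.

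The cost is a few sentences in the SAP and one filter on a flag the SAP already derives from the verbatim term. The exception for worsening requires a check of those few flagged events against the first randomized dose. Because only a date is listed for adverse event onset, worsening on the Baseline date itself may need a query to the site.

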10.3. Prior and Concomitant Medication

Prior and concomitant medications and treatments will be coded using the World Health Organization Drug Dictionary (WHODRUG).

Medications used prior to the date of first dose of study medication will be classified as prior medication, and those used on or after the date of the first study treatment (including Vaseline) will be classified as concomitant medications (including those started prior to the first study

treatment which is ongoing during the study). A medication may be classified as both prior and concomitant.

Medication with a missing or partial start date will be considered as prior medication if the first date implied by the available start date is prior to the first study treatment date. Medications with partial end dates will be considered as concomitant if the last available date implied by the available data is on or after the first study treatment date.

Concomitant medication will be summarised by treatment, Anatomical Therapeutic Chemical (ATC) Level 4, PT, and category (Non-ophthalmic medication and ophthalmic medication), using the Safety Set.

Prior and concomitant medications will be listed. Ophthalmic medications in the study eye will be flagged in the prior and concomitant medication listing. Medication use through the Month 3 visit will be presented at the end of the 3-month study period, and medication use through the end of the safety follow-up period (i.e., through Month 6) will be presented as part of supplemental safety analyses.

10.4. Laboratory Evaluations

Aside from urine pregnancy test, clinical laboratory samples are not collected in the Expansion Cohort.

Urine pregnancy test data will be listed chronologically by patient and visit.

10.5. Best-corrected Visual Acuity; Logarithmic Visual Acuity Chart

BCVA Total letter score, LogMAR (calculated as per [Section 5.2.9](#)), axis, and cylinder will be summarized by time point, and treatment, using absolute values and changes from baseline. Changes in letter scores will also be tabulated as: increases of 5 or more letters, decreases of 5 or more letters, or changes of less than 5 letters; and increases of 10 or more letters, decreases of 10 or more letters, or changes of less than 10 letters. Results for sphere refraction will be tabulated. All results, including Snellen equivalents, will be listed chronologically by patient and visit.

10.6. Vital Signs

Vital signs will consist of systolic and diastolic blood pressure (mmHg) and pulse rate (bpm). Vital signs data (absolute values) will be summarized by parameter, time point, and treatment, and listed chronologically.

10.7. Slit-lamp Biomicroscopy, Including Conjunctival Hyperemia

Slit-lamp biomicroscopy results, including the safety endpoint of conjunctival hyperemia (redness), will be summarized in a shift table as described in [Section 8.3](#). CMH analyses will only be performed for the exploratory efficacy endpoints of study eye erythema and telangiectasias. Results will be listed chronologically.

10.8. Ophthalmoscopy

Lens status (categorized as phakic, pseudophakic, or aphakic) will be summarized by time point, and treatment using a shift table. Cataract status (rated on a 4-point scale from None to Severe), vitreous (normal or abnormal), and fundus (normal or abnormal) will be recorded for phakic eyes, and also tabulated in a shift table. Ophthalmoscopy results, including specifics of any vitreous or fundus abnormalities, will be listed chronologically by patient and visit. Dilation status (dilated or undilated) will be presented in listings, but both dilated and undilated results will be tabulated together in a shift table.

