Discontinue concomitant medication(s) impacting inclusion/exclusion	X								
Contact IVRS/IWRS for patient randomization number		X							
Medication dispensing/return	X (Cohort 1)	X		X	X	X	X	X	
Physician Observation of Drug Application	X (Cohort 1)	X							

BCVA = Best Corrected Visual Acuity; Coh. = Cohort; Expan. = Expansion; OSDI = Ocular Surface Disease Index; SPEED = Standard Patient Evaluation of Eye Dryness; TBUT = tear break up time; VAS = Visual Analogue Scale; PM = Evening, Month = 28 days

a Screening diagnostic procedures are not required to be performed on the same day, and can be performed across multiple days from days -14 to -2. At screening, patients will be asked to report use of artificial tears and all other treatments for MGD and/or DED. Patients should wash out from all medication listed in the inclusion/exclusion criteria. The screening period includes a 2-week, run-in with AZR-MD-001 placebo for Cohort 1. Patients who are re-enrolled following an initial screen failure will receive a new screening number upon re-screen (i.e., sites should not reuse the old number).

b For females of childbearing potential.

c Manifest refraction performed at screening will be used at each visit to obtain BCVA.

d Performed as a sub-study by selected sites and patients and approved by study sponsor.

e Ophthalmoscopy examination will be dilated at screening and undilated for study exit unless dilation is necessary

f Instill dose of medication after completing safety/efficacy measures and ~5 minutes before medication tolerability assessment (see Procedure Manual for more detail).

g TBUT and MGE should be performed by the same individual for a given patient. For the Expansion Cohort, the individual performing the measurement will not be involved in drug dispensing or accountability and should remain masked to the treatment received by the patient.

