5.2 EXCLUSION CRITERIA

- Uncontrolled ocular disease (except for MGD and dry eye disease/keratoconjunctivitis sicca) or uncontrolled systemic disease
- Patient has glaucoma, ocular hypertension, or intraocular pressure (IOP) in either eye at screening ≥ 24 mm Hg as determined by Goldman applanation tonometry (or a COVID-19 compliant device as required by local governance) or has planned insertion/removal of glaucoma filtration shunts/devices during the study
- Corneal abnormality or disorder that impacts normal spreading of the tear film (keratoconus, pterygia, scarring) or corneal integrity
- BCVA worse than 20/40 in either eye at the screening or baseline visit
- Current use of punctal plugs, anticipated insertion during the study, or a history of punctal cauterization in either eye at any time prior to the screening visit or anticipate such a procedure during the study
- Keratoconjunctivitis sicca secondary to destruction of conjunctival goblet cells as occurs with vitamin A deficiency or scarring, such as that with cicatricial pemphigoid, alkali burns, Stevens-Johnson syndrome, trachoma, or irradiation
- Keratoconjunctivitis sicca secondary to aqueous deficient DED
- Active ocular infection (bacterial, viral, or fungal) at the screening or baseline visits
- Corneal, conjunctival, or eyelid inflammation (including allergic, vernal, or giant papillary conjunctivitis and mucous membrane pemphigoid) that in the judgment of the investigator may interfere with the study results or the ability of patients to complete the treatment period
- Recent (within the past 3 months of the screening visit) ocular surgery, trauma, herpes, or recurrent inflammation
- Contact lens use anticipated during the study
- Periocular application of makeup during the study (e.g., mascara or eyeliner) that the investigator feels could interfere with the signs and symptoms of either MGD or Evaporative DED or tattooing of the lids
- Use of any type of scleral lenses or sealed compartment ocular frames within 2 months of the screening visit, or planned use during the study
- Use prohibited medications (topical, topical ophthalmic, systemic and/or injectable)

during the appropriate pre-study wash-out period and during the study.

- Unwilling to abstain from the use of systemic medications known to cause dryness for the study duration that is not used on a stable dosing regimen for at least 30 days prior to the baseline visit.

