- Unwilling to abstain from the use of systemic or topical treatments for MGD or dry eye for the study duration (Including over-the-counter [OTC] artificial tears, ocular lubricants, or dietary supplements known to impact ocular surface health)
- Eyelid abnormalities that affect normal lid function in either eye other than those caused by meibomian gland dysfunction
- Diagnosis of hepatitis C infection, human immunodeficiency virus (HIV) infection, sarcoidosis, amyloidosis, active tuberculosis, or graft versus host disease
- History of anterior segment surgery or trauma that could affect corneal sensitivity (e.g., cataract surgery or any surgery involving a limbal or corneal incision) in either eye within the 12 months prior to the screening visit
- Planned anterior segment surgery (e.g., cataract surgery or any surgery involving a limbal or corneal incision) in either eye during the study period
- Meibography score at the screening visit of 4 (greater than 75% partial glands using the gestalt grading system)
- Corneal staining ≥ 3 (between 33 and 100 dots) using the Oxford Scheme
- Schirmer's tear test without anesthesia ≤ 5 mm in either eye at the baseline visit
- Known allergy or sensitivity to fluorescein, lissamine green, or the study medication or its components
- Use of medicated shampoos containing selenium (e.g., Selsun Blue, Exsel, Selsum, and Seleen) following the screening visit
- Patient is unlikely to follow study instructions or to complete all required study visits or has a condition or situation that in the investigator's opinion, may put the patient at significant risk, may confound the study results, or may interfere significantly with the patient's participation in the study
- Patient is an employee at the investigational site or is related to any member of the study staff
- Patient cannot tolerate multiple blood draws (Cohort 1 only)
- Pregnant, nursing, or females of childbearing potential and not utilizing adequate birth control measures
- Positive urine pregnancy test at the screening visit
- Participation in another clinical trial involving a therapeutic drug or device within the past 30 days
- Enrollment in a previous Stage of the current study or other Azura study using AZR-MD-001
- The patient has a screening laboratory result (e.g., hematology, serum chemistry, or urinalysis) that, in the opinion of the investigator, would make the patient unsuitable for study participation (Cohort 1 only)

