10.9. Intraocular Pressure

IOP results will be categorized as <18, 18-25, or >25 mmHg separately in the study eye and non-study eye and summarized using a shift table. Results will be listed chronologically by patient and visit.

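### SAP 10.8 as worded leaves pseudophakic and aphakic eyes out of the vitreous and fundus safety tables, and SAP 10.9 reduces IOP to a three-bin shift that hides rises from 18-23 to 24-25 mm Hg

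*SAP*

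**What the plan says.** **Ophthalmoscopy.** SAP 10.8 opens by expecting all three lens states: "Lens status (categorized as phakic, pseudophakic, or aphakic) will be summarized by time point". Its next sentence takes cataract status, vitreous and fundus together and says of the last two: "vitreous (normal or abnormal), and fundus (normal or abnormal) will be recorded for phakic eyes, and also tabulated in a shift table". It then plans a listing: "Ophthalmoscopy results, including specifics of any vitreous or fundus abnormalities, will be listed chronologically by patient and visit". The corresponding outputs are Tables 35A (lens status) and 35B (ophthalmoscopy details) at Month 3, and 35.1A and 35.1B at Month 6.

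The protocol describes the examination in footnote e of its schedule of activities: "Ophthalmoscopy examination will be dilated at screening and undilated for study exit unless dilation is necessary". Lens status plays no part in that instruction.

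**IOP.** SAP 10.9 says "IOP results will be categorized as <18, 18-25, or >25 mmHg separately in the study eye and non-study eye", summarised in a shift table (Tables 36 and 36.1), with individual results listed (Listings 25 and 25.1). It plans no arm-level mean or median and no change from screening. Protocol 5.2 excludes patients with "intraocular pressure (IOP) in either eye at screening ≥ 24 mm Hg".

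Both assessments are safety endpoints in SAP 3.2. Both are scheduled at screening, Month 3 and Month 6 only, so the screening result is the reference for any shift.

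**The concern.** A vitreous or fundus finding can be graded whatever the lens status, so the phakic condition has an obvious reason for cataract and none for the other two items. SAP 12, which lists changes from the protocol, does not mention it. Followed as written, it removes a recognisable group of eyes from the arm comparison of a named safety endpoint. The condition attaches to recording as well as tabulation, so the loss could reach data collection.

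For IOP, a numeric safety measure is reduced to three bins, one of which spans the protocol's entry limit. Some rises inside a bin leave no trace in the only planned summary by arm. A modest average rise in an active arm could be missed there, although the data to show it will already have been collected.

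**Working it through.** **Step 1. Can non-phakic eyes be in the trial?**

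- Protocol 5.1 admits patients aged 18 or older and sets no upper age.
- Protocol 5.2 excludes "History of anterior segment surgery or trauma that could affect corneal sensitivity (e.g., cataract surgery or any surgery involving a limbal or corneal incision"), but only when it fell in the 12 months before screening. Cataract surgery before that is not excluded by this criterion.
- SAP 10.8 itself provides pseudophakic and aphakic categories.

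Such eyes are therefore both eligible and expected.

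**Step 2. Where do their results appear under SAP 10.8 as worded?**

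| Output | Phakic eyes | Pseudophakic or aphakic eyes |
|---|---|---|
| Lens status shift (35A, 35.1A) | included | included |
| Cataract shift | included | not applicable |
| Vitreous and fundus shift (35B, 35.1B) | included | **absent** |
| Ophthalmoscopy listing (24, 24.1) | included | included only if the eCRF collects the items for them |

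The last row cannot be settled, because the eCRF is not in the documents. If it applies the phakic condition, there is nothing to list. If the condition was meant for cataract status only, the listing is complete and the sentence is loosely drafted.

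**Step 3. Which IOP rises does the three-bin table hide?** The plan gives no figure to reproduce here, so I enumerated whole mm Hg values.

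- Inputs: SAP 10.9 bins (below 18; 18-25; above 25), and eligible screening values below 24 (protocol 5.2).
- Assumed range ends: 8 for screening and 40 for follow-up. They do not affect which pairs are hidden.
- Rule: a rise is hidden when the screening and follow-up values fall in the same bin.

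| Screening | Follow-up | Pairs | No shift shown |
|---|---|---|---|
| 18-23 | 24-25 | 6 × 2 = 12 | 12 |
| 18-23 | 26-40 | 6 × 15 = 90 | 0 |
| 8-17 | 24-40 | 10 × 17 = 170 | 0 |
| Total | | 272 | 12 |

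These are counts of cells, not shares of patients.

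- 18 to 25 is a rise of 7 mm Hg (7/18 = 39%) and shows no shift.
- 17 to 18 is a rise of 1 mm Hg and shows a shift.
- 17 to 24 shows a shift, but lands in the same cell as 17 to 18, so the two cannot be told apart.

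**Step 4. Is IOP summarised elsewhere by arm?** The Appendix 4 and Appendix 5 lists give IOP one table each, both shift tables. BCVA, by contrast, is given values and changes from baseline (SAP 10.5), and vital signs are given absolute values (SAP 10.6).

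**The case against.** **The phakic phrase is probably a misplaced modifier.** The listing sentence that follows it and the protocol's footnote e carry no such limit. This is plausible, and it rules out asserting that non-phakic eyes certainly have no posterior-segment result. It does not rescue the text: a programmer following SAP 10.8 would drop those eyes, and the intended reading needs the same correction.

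**The IOP shift table is what the protocol planned.** Protocol Table 3-1 names shift tables for IOP and ophthalmoscopy, and protocol 9.4.4 leaves detailed methods to the analysis plan. This stands: the SAP does not depart from the protocol, and the request is to add to the table, not replace it. SAP 5.1 also says continuous data are in general summarised descriptively. However, SAP 10.9 is the specific rule, and the table lists contain no such IOP output.

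**Any binning hides some rises and exaggerates others.** True, and moving a cut to 24 would not cure it: 18 to 23 would then be hidden while 23 to 24 registered. This is why the remedy is a continuous summary and not a different cut-point.

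**Nothing is lost, since values are listed and clinically significant worsening is reportable as an adverse event** (protocol 8.3.1). This stands for individual patients. A listing does not compare arms, and adverse events capture only what an investigator judged significant.

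**Dilation.** A reader might infer a further flaw from "both dilated and undilated results will be tabulated together in a shift table", since screening is dilated and exit usually is not. The documents do not support pressing this. The pooling is disclosed and dilation status is listed. The schedule is the same in every arm. The footnote covers screening and exit only, so the Month 3 practice in the Expansion Cohort is unstated. Splitting the table by follow-up dilation would still compare against a dilated screening examination.

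**Conclusion.** The point holds as a minor gap in safety reporting, in two parts.

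1. SAP 10.8 as worded omits eligible, expected non-phakic eyes from the vitreous and fundus shift tables. Whether the data are also uncollected depends on the eCRF, which cannot be seen.
2. SAP 10.9 gives no arm-level IOP values or change from screening. Among whole-number crossings of 24 mm Hg, the shift table hides exactly those from 18-23 to 24-25.

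Three stronger readings are tempting and not supported:

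- **That any rise past 24 mm Hg goes unseen.** Every rise to 26 or more registers, as does every rise past 24 from below 18.
- **That 24 mm Hg is a safety limit during treatment.** It appears only as a screening exclusion, so the bins contradict nothing in the protocol.
- **That a patient count can be put on the lens restriction.** The documents give no frequency of pseudophakia. The restriction also works by eye, so a patient with one operated eye keeps a tabulated result for the other.

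The primary efficacy analysis, power and type I error are not touched.

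**What to change.** **SAP 10.8.** Attach the phakic condition to cataract status alone, and state that vitreous and fundus are recorded and tabulated for every eye regardless of lens status. If the restriction is intended, give the reason. Carry the change into Tables 35B and 35.1B. Check the eCRF and remove any skip that suppresses vitreous and fundus entries in non-phakic eyes.

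**SAP 10.9.** Keep the shift table. Add to Tables 36 and 36.1 descriptive IOP values (n, mean, SD, median, minimum, maximum) and change from screening, by arm and separately for study and non-study eye, at Month 3 and Month 6 (Table 36 through Month 3; Table 36.1 adds Month 6).

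**Cost.** SAP wording, a few table rows and possibly one eCRF edit. The IOP addition uses data already scheduled for collection. Vitreous and fundus need no new examination, because ophthalmoscopy is already scheduled for all patients.
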